#### **Systemic chemotherapy in metastatic adenocarcinoma of the cervix:**

Systemic chemotherapy is the recommended treatment for metastatic or recurrent adenocarcinoma of the cervix not amenable to irradiation or surgery. However, there is limited data on the treatment of recurrent cervical adenocarcinoma because of its infrequent occurrence and the paucity of active chemotherapeutic agents. The available data on the use of chemotherapy in cervical adenocarcinoma comes from clinical trials, many of which have been conducted by the Gynecologic Oncology Group (GOG) [12-24]. Single agent trials in patients who had received prior irradiation and/or chemotherapy demonstrated evidence of activity for six chemotherapeutic agents: cisplatin, piperazinedione, ifosfamide gallium nitrate, 5-FU plus leucovorin and paclitaxel (Table 1). Agents that have been tested and deemed ineffective include: CCNU, methyl-CCNU, mitoxantrone, etoposide (VP-16), teniposide (VM-26), vinblastine, aminothiadiazole, echinomycin, ICRF-159 (Razoxane), dianhydrogalactitol, diaziquone (AZQ) and tamoxifen.

Several studies have noted the activity of paclitaxel in cervical adenocarcinoma. The first published suggestion that paclitaxel may be active in cervical adenocarcinoma came from a study in which paclitaxel was used as part of a combination chemotherapy regimen principally in the neoadjuvant setting [23]. Whereas a prior study had noted an overall pathologic response rate of 47% with weekly cisplatin and epirubicin as neoadjuvant therapy [22], Lissoni and colleagues reported that the addition of paclitaxel to this neoadjuvant regimen resulted in a pathologic response rate of 65% [23]. Subsequent to this, single agent activity was reported in a phase 2 GOG study of 46 patients treated with 170 mg/m^2 paclitaxel (or 130 mg/m^2 for patients with prior pelvic irradiation) given as a 24 hour infusion every three weeks [16]. The overall response rate for the 42 assessable patients was 31% (4 CRs and 9 PRs). In addition, Ota et al

reported a single case of metastatic cervical adenocarcinoma with a complete response after twenty cycles of weekly paclitaxel [17].

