**Table 1: Chemotherapy for Adenocarcinoma of the Cervix**

Single Agent Chemotherapy				
Author (Year)	Agent	Pts	RR 	Comments
Thigpen (86) 	Cisplatin	12 	25%	Only 50 mg/m  q3wks; lowest WBC: 1600/mL
Thigpen (86) 	Piperazinedione	6 	17%	9 mg/m  q 3wks; drug not available
Sutton (93) 	Ifosfamide	41 	15%	1.5 g/m  /d x 5d (1.2 if prior RT); 28 pts with adenocarcinoma
Malfetano (95) 	Gallium Nitrate	26 	11%	750 mg/m  q3wks; 21 pts with adenocarcinoma
Look (97) 	5-FU + High Dose Leucovorin	43	13%	370 mg/m  qd x 5d q4wks; G3/4 ANC: 53%
Curtin (01) 	Paclitaxel (24h infusion q3 weeks)	42 	31%	170 mg/m  ; 130 mg/m  if prior pelvic RT; G3/4 ANC: 74%
Ota (01) 	Paclitaxel (weekly)	1	1/1	Case report. 70 mg/m  by 1h infusion
Combination Chemotherapy Regimens				
Author (Year)	Agent	Pts	RR	Comments
Kavanagh (87) 	Cisplatin/5-FU/Doxorubicin	24	42%	Cis: 50-60mg/m  ; 5-FU: 500-800mg/m  ; Dox: 40-50mg/m  G3/4ANC: 38%
Bates (91) 	Cisplatin/Mitomycin C	1	1/1	Case report. Cis: 50 mg/m  q3wks; MMC: 10 mg/m  /q6wks
Fanning (95) 	Cisplatin/5-FU/Ifosfamide	9 	78%	Cis: 90 mg/m  /5-FU: 1500 mg/m  ; Ifos: 3 g/m  ; G4ANC:6%
Umesaki (99) 	Cisplatin/Mitomycin/Etoposide	31	16%	Cis: 50 mg/m  ; MMC: 10 mg/m  ; E: 100 mg/m  x3; G3/4ANC: 45%
Zanetta (97) 	Cisplatin/Epirubicin	22	50%	Neoadjuvant. Cis: 50 mg/m  qwk; Epi: 70 mg/m  q3wks; +GF; G3/4ANC: 45%
Lissoni (97) 	Cisplatin/Epirubicin/Paclitaxel	19	53%	17 neoadjuvant. Cis: 50 mg/m  ; Epi: 70 mg/m  Pac: 135-175 mg/m  ; G3/4 ANC: 60%
Saito (04) 	Cisplatin/Aclacinomycin A/Mitomycin C	16	75%	IV or Intra-arterial for localized disease

Some responses have been recalculated from that reported based on currently accepted criteria and histologic breakdown

Data reported for "Nonsquamous Carcinoma". Insufficient information given to determine activity in adenocarcinoma subtype

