## 2 ELIGIBILITY ASSESSMENT AND ENROLLMENT

### 2.1 ELIGIBILITY CRITERIA

#### 2.1.1 Inclusion criteria:

Patients must fulfill all of the following criteria to be eligible for study admission:

1. Age  $\geq$  18 years.
2. Histologic or cytologic confirmation of cervical carcinoma, squamous or non-squamous. Within the non-squamous cohort is adenocarcinoma and adenosquamous as well as non-squamous (not otherwise specified).
3. Subjects with unresectable recurrent cervical cancer are eligible.
4. Measurable disease that can be assessed using RECIST criteria.
5. Performance Status ECOG 0-2.
6. Life expectancy of 3 months or greater.
7. Suitable candidate for receiving planned therapy as evidenced by screening laboratory assessments of hematologic, renal, hepatic, and metabolic functions: platelet count  $\geq$  75,000/mm^3, absolute granulocyte count (AGC)  $\geq$  1,000/mm^3, serum creatinine  $\leq$  1.6 or a measured creatinine clearance  $\geq$  40 ml/min, SGPT and SGOT  $\leq$  2.5 x NL, and total bilirubin  $\leq$  1.5 x NL (in patients with clinical evidence of Gilbert's disease,  $\leq$  3 x NL).
8. Note: A diagnosis of Gilbert's disease will be made in the presence of (1) unconjugated hyperbilirubinemia noted on several occasions; (2) normal results from CBC count, reticulocyte count, and blood smear; (3) normal liver function test results; and (4) an absence of other disease processes that can explain the unconjugated hyperbilirubinemia.
9.  $\geq$  4 weeks from prior radiation, intravenous chemotherapy or immunotherapy;  $\geq$  6 weeks from prior nitrosourea;  $\geq$  2 weeks from a prior "phase 0 study".
10. No serious intercurrent medical illness.
11. The ability to understand and willingness to sign a written informed consent form, and to comply with the protocol.
12. Prior therapy with cisplatin or carboplatin is required.

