#### 2.1.2 Exclusion criteria:

Patients with any of the following will be excluded from study entry:

1. Pregnant or nursing women are not eligible; neither are women of childbearing potential unless using effective contraception as determined by the patient's physician.
2. Patients with a history of CNS metastases, because symptoms/signs of progressive disease may be confused with drug-related toxicities, unless control has been achieved with either radiation or surgical resection at least three months prior to enrollment on study.
3. Patients who are poor medical risk because of other non malignant systemic disease or active, uncontrolled infection.

4. HIV positive patients will be considered for eligibility; as long as they are not receiving antiretroviral drugs with strong CYP3A4 inhibitory activity (see 3.6 and Appendix C).
5. Prior craniospinal radiation, or total body irradiation (TBI).
6. Patients receiving other investigational drugs, or strong CYP3A3 inhibitors (see Section 3.6 for details) that cannot be discontinued or substituted.
7. CTCAE Grade 2 or greater motor or sensory neuropathy.
8. Known prior severe hypersensitivity reactions to agents containing Cremophor® EL.
9. Women with localized disease who are potentially curable through surgical resection.

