### Within 7 days of study entry\*:

6. Complete history and physical examination with documentation of measurable disease and performance status.
7. Laboratory tests: CBC with differential and platelet count, and CHEM 20 Panel.
8. Urine or serum pregnancy test in women of childbearing potential.

\*Any abnormal laboratory tests of clinical significance (CHEM 20 Panel) should be repeated within 48 hours of study initiation. The principal investigator should be contacted to determine if the test(s) need to be repeated.

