#### 3.3.2 Treatment modifications for hematologic toxicities and delay in start of cycle

Doses will be modified if the start of a cycle is delayed more than two weeks (in all cycles after the first cycle, the day 1 dose will be administered only when the ANC is greater than 1000/mm^3 and the platelet count is above than 75,000/mm^3). There will be no dose modification for a delay of two weeks or less.

Doses will also be modified based upon the nadir from the previous cycle according to the following guidelines.

Toxicity:	Dose Adjustment:
ANC $\leq$ 500/mm  for $\geq$ 4 days	Reduce ixabepilone one dose level
Platelet count $\leq$ 50,000/mm 	Reduce ixabepilone one dose level
Delay in starting cycle > 2 weeks	Reduce ixabepilone one dose level

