APPENDIX B: Study Calendar

EVALUATIONS REQUIRED PRE, DURING, AND POST THERAPY:

	A	B	C	D	E	F
Complete medical history		X				
Interim medical history				X		X
Physical examination		X		X		X
Weight and height		X		X		
Vital signs		X		X		X
ECOG performance status	X	X		X		X
Urine pregnancy test		X				
HIV Screen/Hepatitis B and C Screen	X					
Staging laboratory evaluation		X			X	X
Routine laboratory evaluation		X		X		X
CBC with differential and platelet count		X	X	X		X
Staging imaging studies	X				X	X
Biopsy & Research bloods (if indicated)*				✗		✗

A: Within 4 weeks prior to initiating therapy

B: Within 1 week prior to initiating therapy

C: Weekly or twice weekly during period of anticipated neutropenia

D: Every cycle

E: Every 2 cycles (Imaging studies and chest radiograph every third cycle after cycle 6)

F: Study termination.

\*Biopsies will be obtained after consent but before Day 1 dosing, and again on either Day 4 or Day 5. Biopsies are optional.

Research Labs for tubulin polymerization will be obtained prior to the Cycle 1 Day 1 drug infusion, and 1, 8 and 24 hours after Day 1 infusion start, and on either Day 4 or 5, within 1 hour of the biopsy. The research labs will only be done in those patients who have biopsies performed.

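### Inclusion item 9 ties the 4-week chemotherapy washout to the intravenous route, so a patient whose last treatment was a marketed, non-intravenous, non-nitrosourea cytotoxic outside a phase 0 study has no required interval before entry

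*Combined protocol and SAP*

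**What the plan says.** Section 2.1.1, item 9, is the only washout rule for prior anticancer drugs. It asks for a minimum of "4 weeks from prior radiation, intravenous chemotherapy or immunotherapy", then 6 weeks after a nitrosourea and 2 weeks after a phase 0 study. The last two carry no route restriction; the chemotherapy interval does.

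Item 7 of the same section sets the laboratory thresholds, introduced as "Suitable candidate for receiving planned therapy as evidenced by screening laboratory assessments of hematologic, renal, hepatic, and metabolic functions". They include an absolute granulocyte count of at least 1,000/mm³ and platelets of at least 75,000/mm³. Item 12 requires prior cisplatin or carboplatin and puts no limit on other earlier agents or their route.

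Exclusion 6 (section 2.1.2) covers "Patients receiving other investigational drugs, or strong CYP3A3 inhibitors". It concerns drugs the patient is still receiving and gives no interval for marketed agents.

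**The concern.** A washout before a myelosuppressive regimen lets the marrow effect of the previous drug declare itself and recover. Item 9 gives that protection after intravenous chemotherapy, and the protocol offers no reason why another route should remove it. As written, even a phase 0 study carries a longer required interval (2 weeks) than a treatment course of a marketed oral or intra-arterial cytotoxic.

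A patient whose counts are still falling after such a drug could meet the screening thresholds and start cycle 1 while the earlier toxicity is still developing. The study drug adds its own effect. As background only, section 1.2.4 describes a 37-patient breast cancer trial at this dose and schedule in which grade 3 and 4 toxicities included neutropenia in 35% and febrile neutropenia in 14%. Those figures say nothing about washout. Section 3.3.1 allows one dose reduction, so a nadir partly due to an earlier drug could use it up. That is a possible consequence; the documents do not show that it would happen.

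**Working it through.** The plan gives no figure for this point, so the check is a comparison of its rules.

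**Step 1: required interval by type of last treatment**

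| Last treatment | Required interval | Source |
|---|---|---|
| Nitrosourea | 6 × 7 = 42 days | Item 9 |
| Intravenous chemotherapy | 4 × 7 = 28 days | Item 9 |
| Phase 0 study agent | 2 × 7 = 14 days | Item 9 |
| Other investigational drug, still being received | Not eligible | Exclusion 6 |
| Marketed, non-intravenous, non-nitrosourea cytotoxic | None stated, so 0 days | No rule |

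The last row is the gap. It applies when that drug is the most recent treatment. If the last regimen also had an intravenous component, the 28 days run from that component.

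**Step 2: does another section supply an interval?**

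- Section 3.6 (concurrent therapies) restricts CYP3A4 inhibitors and grapefruit juice. It has no rule on other cytotoxics.
- Section 3.8 bars concurrent radiation only.
- Section 2.2 calls for a blood count within 7 days of study entry, and column B of Appendix B places it "Within 1 week prior to initiating therapy". The repeat rule there reads "Any abnormal laboratory tests of clinical significance (CHEM 20 Panel) should be repeated within 48 hours of study initiation", which names the chemistry panel and not the blood count.
- Section 3.3.2 sets a Day 1 count threshold, but "in all cycles after the first cycle, the day 1 dose will be administered only when the ANC is greater than" 1,000/mm³ shows that it begins with cycle 2.

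None of these is an interval. For this patient the item 7 screening count is the last count with a written threshold before the first dose. That is equally true after intravenous chemotherapy, but there 28 days have already passed.

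**Step 3: what mitigates the gap?**

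- Section 3.5.4: twice-weekly blood counts in cycles 1 and 2. The stated response to very low values is more frequent counts.
- Section 3.3.2: a nadir ANC of 500/mm³ or below for at least 4 days, or platelets of 50,000/mm³ or below, reduces the next cycle's dose.
- Section 4, item 1: management of febrile neutropenia, with growth factors permitted under ASCO guidelines.
- Sections 3.9 and 6.4: investigator discretion on stopping and on entry.

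The on-treatment rules act after dosing has begun. They limit harm but do not delay the first dose.

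**Step 4: does the point touch the design's error rates?**

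Inputs from section 5.4.1: 12 patients then 37 per cohort, stop at 0/12, active at 4/37 or more, p0 = 0.05, p1 = 0.20.

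- Early termination at p0: 0.95^12 = 0.540, which reproduces the stated 0.54.
- Probability of declaring activity: the sum over x = 1 to 12 of P(X1 = x) × P(X2 ≥ 4 − x), with X1 ~ Bin(12, p) and X2 ~ Bin(25, p). This gives 0.0935 at p = 0.05 and 0.902 at p = 0.20, within the planned 0.10 and 0.90.

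These depend only on the sample sizes, cut-offs and response probabilities. A reworded washout clause changes none of them.

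**The case against.** The strongest reply is that the exposed group is narrow and the documents do not show that it exists. Platinum pretreatment is required, and any recent intravenous component already starts the 4-week clock. What remains are patients whose latest cytotoxic was marketed, non-intravenous and not a nitrosourea, and who still pass the organ-function, performance-status and intercurrent-illness criteria. Graded intervals are also a matter of judgement: nothing in the documents shows that 28 days is right for every route, and waiting has a cost for patients described in section 6.3.5 as having no standard options left. All of this stands. It limits the size of the point and is why the sponsor should be free to choose a shorter interval for oral agents. It does not justify silence, which leaves the interval at zero.

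Four stronger readings are tempting, and the documents do not support them.

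- *Every non-intravenous drug except nitrosoureas escapes.* It does not: the phase 0 interval has no route limit, and exclusion 6 bars patients still receiving other investigational drugs.
- *The week-old blood count and the absent cycle 1 count threshold are part of this defect.* Both apply equally after intravenous chemotherapy, so neither is specific to route.
- *The protocol's own literature table shows an affected population.* The only non-intravenous regimen identified there, in 16 patients, is annotated "IV or Intra-arterial for localized disease". Such patients would probably be well past 4 weeks at recurrence. Etoposide appears in section 1.2.1 among agents judged ineffective in cervical adenocarcinoma, with no route given.
- *Carry-over from the earlier drug biases the response rate.* Nothing in the documents allows that to be estimated or shown.

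**Conclusion.** The gap in the written rule is real and the point is minor: a cheap improvement to patient safety. Item 9 permits entry at 0 days in the case defined above, against 28 days after intravenous chemotherapy. The number of such patients is unknown and probably small, and the documents give no basis for computing the added marrow risk. No effect on the primary conclusion is shown.

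This rests on the literal reading that the route qualifies the chemotherapy interval, and on there being no further washout rule outside the documents. Confidence is high about what the rule says. It does not extend to how often, or how badly, a patient would be harmed.

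**What to change.** Reword the first clause of item 9 to: *≥ 4 weeks from prior radiation, chemotherapy (any route) or immunotherapy*. Keep the 6-week nitrosourea and 2-week phase 0 intervals. If the sponsor judges that oral agents need less, state that shorter interval explicitly. Any interval for targeted or hormonal drugs can be left to the sponsor.

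The cost is one eligibility clause and the matching line of the registration checklist, with no change to sample size or analysis. A few patients may wait up to 28 days. Against the 3-month minimum life expectancy in item 6, taken as about 91 days, that is at most 28/91 = 0.31, or about 31%. Patients coming off intravenous chemotherapy are already asked to wait as long.

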#### 2.1.2 Exclusion criteria:

Patients with any of the following will be excluded from study entry:

1. Pregnant or nursing women are not eligible; neither are women of childbearing potential unless using effective contraception as determined by the patient's physician.
2. Patients with a history of CNS metastases, because symptoms/signs of progressive disease may be confused with drug-related toxicities, unless control has been achieved with either radiation or surgical resection at least three months prior to enrollment on study.
3. Patients who are poor medical risk because of other non malignant systemic disease or active, uncontrolled infection.

4. HIV positive patients will be considered for eligibility; as long as they are not receiving antiretroviral drugs with strong CYP3A4 inhibitory activity (see 3.6 and Appendix C).
5. Prior craniospinal radiation, or total body irradiation (TBI).
6. Patients receiving other investigational drugs, or strong CYP3A3 inhibitors (see Section 3.6 for details) that cannot be discontinued or substituted.
7. CTCAE Grade 2 or greater motor or sensory neuropathy.
8. Known prior severe hypersensitivity reactions to agents containing Cremophor® EL.
9. Women with localized disease who are potentially curable through surgical resection.

## 2.2 RESEARCH ELIGIBILITY EVALUATION

1. Pathological confirmation of diagnosis by the Laboratory of Pathology, CCR, NCI.

### Within 4 weeks of study entry:

2. Imaging studies: PA and lateral chest X-ray; CT or MRI scans as medically indicated.
3. Metastatic bone series, bone scan, or nuclear scans as medically indicated.
4. HIV screen.
5. Urinalysis.

### Within 7 days of study entry\*:

6. Complete history and physical examination with documentation of measurable disease and performance status.
7. Laboratory tests: CBC with differential and platelet count, and CHEM 20 Panel.
8. Urine or serum pregnancy test in women of childbearing potential.

\*Any abnormal laboratory tests of clinical significance (CHEM 20 Panel) should be repeated within 48 hours of study initiation. The principal investigator should be contacted to determine if the test(s) need to be repeated.

## 2.3 PATIENT REGISTRATION AND TREATMENT RANDOMIZATION

1. On-study: [name], RN [contact], [contact]) or her designee must be notified before entering any patients on study. Authorized staff must register an eligible candidate with NCI Central Registration Office (CRO) within 24 hours of signing consent. A registration Eligibility Checklist from the web site (<http://intranet.cancer.gov/ccr/welcome.htm>) must be completed and faxed to [contact]. After confirmation of eligibility at Central Registration Office, CRO staff will call pharmacy to advise them of the acceptance of the patient on the protocol prior to the release of any investigational agents. Verification of Registration will be forwarded electronically via e-mail. A recorder is available during non-working hours. *Please note, it is very important for all registrars to acquire encrypted e-mail from NIH Help Desk, since the verification of registration includes patient's information.*
2. Off-study: Authorized staff must notify Central Registration Office (CRO) when a patient is taken off-study. An off-study form from the web site (<http://intranet.cancer.gov/ccr/welcome.htm>) main page must be completed and faxed to [contact].

3. This trial does not involve randomization. Patients will be stratified according to histology: (1) squamous cell cohort and (2) non-squamous cell cohort consisting of adenocarcinoma, adenosquamous and non-squamous (not otherwise specified).

### 3 STUDY IMPLEMENTATION

#### 3.1 STUDY DESIGN

This is a phase II trial designed to determine the activity of ixabepilone administered daily x 5, every three weeks, in women with cervical carcinoma. The dose will be 6 mg/m^2/day, daily x 5, for a total dose per cycle dose of 30 mg/m^2. There will be no dose escalations. If indicated the dose may be reduced to 4.5 mg/m^2/day level. Every attempt to administer cycles at intervals of 3 weeks will be made. Following cycle 6, at the discretion of the PI, cycles may be extended to 4 or 5 weeks in duration to accommodate neurosensory changes and or fatigue. This will be determined on a case-by-case basis.

Research biopsies will be done prior to Day 1 and post Day 4 or 5 dosing to assess tubulin polymerization and the extent of PARP activation. On Day 4 or 5, the patient will receive ixabepilone in the morning hours and have the biopsy within 4 hours of completing the infusion.

The primary and secondary endpoints for the study are tumor response per RECIST and the degree of tubulin polymerization as it relates to cellular death pathways. Patients will be evaluated for tumor response after every 2 cycles. Biopsies will be obtained during cycle one only, before and after chemotherapy to obtain tubulin polymerization data and to examine other molecular markers.

#### 3.2 DRUG ADMINISTRATION

##### 3.2.1 General guidelines

Chemotherapy may be administered as an inpatient or as an outpatient. Inpatient administration may be chosen if this is in the patient's best interest. Administration may be through either a peripheral IV site or a central venous access catheter. Both options are acceptable. Care should be taken to avoid extravasation, since this drug is likely to be a vesicant. If a catheter is used a single lumen central venous access catheter is sufficient and should be in place before initiating therapy. Placement may be arranged before the start of therapy, or a catheter may be placed immediately before a cycle.

